4.7.3. Treatment Administration

Initial treatment with the IP in the ARQ-151-313 will occur on Day 1 (Day 29 from the preceding study). ARQ-151 cream 0.15% or ARQ-151 cream 0.05% is administered once daily (unless entering BIW maintenance therapy) as a topical product to cover the skin surface at an application rate of approximately 2 mg/cm².

At Day 1 visit, the study staff will redemonstrate to the subject/caregiver(s) how to apply ARQ-151 cream using the first tube from the kit that is assigned to the subject. Study site staff will be retrained to ensure a unit dose (a pea size unit of ARQ-151 cream will cover approximately 1% BSA) is properly squeezed from the tube and applied to atopic dermatitis lesion(s) as a thin film and rubbed in using the index and middle finger, rubbing in thoroughly but gently, until the ‘white’ has disappeared. The subject/caregiver will then practice squeezing a similar amount onto their index and middle finger and apply a thin film to other areas to be treated. At Day 1, the study staff will ensure that the subject/caregiver’s application technique is correct and that a thin layer is applied as instructed (which represents an application rate of approximately 2 mg/cm²).

Re-training will be conducted at subsequent visits as needed (i.e., if the returned tube(s) weighs substantially different than the expected weight).

For the first 4 weeks of study ARQ-151-313, all subjects will apply study medication QD in the areas identified and treated as per the body diagram in the preceding study (ARQ-151-311/312/315). Beginning at the Week 4 visit, any subject who achieves vIGA-AD of ‘0-clear’ as confirmed by the Investigator at a scheduled or unscheduled clinic visit, will switch to twice weekly (BIW) maintenance treatment. For maintenance therapy, study medication will be applied on two nonconsecutive days per week (e.g. Monday and Thursday) to areas commonly

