and/or most recently affected by AD, and any areas where AD is developing. Subjects receiving maintenance treatment who experience AD worsening (signs and symptoms) for 1 week despite dosing twice weekly will phone the clinical study site, resume daily dosing, and complete the subject diary accordingly. The phone call (but not a clinic visit) is required to resume daily dosing. At clinic visits, subjects receiving maintenance treatment may continue twice weekly maintenance dosing if vIGA-AD is either '0-clear' or '1-almost clear'. Subjects will resume daily dosing if vIGA-AD ≥ 2 , and can resume daily dosing if signs/symptoms of AD are not adequately controlled with maintenance therapy despite vIGA-AD of '1-almost clear'.

Note:

- For daily dosing from Week 4 onwards, study medication should be applied to any areas where AD is active or developing, and areas commonly and/or most recently affected by AD.
- All subjects should apply medication each evening (unless on BIW maintenance therapy) except on Day 1 when medication application will be done on site. If the subject takes an evening shower/bath, the ARQ-151 cream can be applied as soon as the skin is nearly dry, but no later than 20 minutes before going to bed. Subjects are not to wash areas where ARQ-151 cream has been applied until at least 2 hours after study drug application.
- Caregivers should wash their hands with soap and water after applying IP to a child.
- Parents/guardians/caregivers who are pregnant, or women of childbearing potential who are trying to become pregnant, or who are breastfeeding, or planning to breastfeed during the study should avoid accidental exposure by either avoiding applying investigational product or by wearing gloves during its application.
- New lesions that develop during the study should be treated (except scalp). An unscheduled visit is not required for starting treatment of new lesions.

Each investigational product tube will be weighed prior to dispensing at the Day 1 visit and at each subsequent visit. Investigational product tubes must be returned by subjects at each study visit, both empty and full, and will be weighed. If the subject's actual use is substantially different than the expected use for the subject's BSA (see IP Handling Plan), the subject/caregiver will be retrained on the study drug application technique.

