5.1.11. Local Tolerability Assessment

The Investigator Local Tolerability Assessment will be performed according to the Schedule of Visits and Assessments ([Section 1.3](#)).

At Day 1 only, local tolerability assessments should be recorded prior to study drug application for the Investigator assessment of skin irritation (Berger and Bowman skin irritation score).

Application site reactions will be graded at each timepoint. Irritation reactions are graded using the scale detailed in the following section ([Berger 1982](#)). **Reactions at the site of product application, which may occur post-Baseline, should be differentiated from the preexisting inflammation associated with the subject's atopic dermatitis.**

The investigator assessments will be conducted by the investigator or a properly trained and designated subinvestigator in the clinic.

Dermal Response

0. no evidence of irritation
1. minimal erythema, barely perceptible
2. definite erythema, readily visible; minimal edema or minimal papular response
3. erythema and papules
4. definite edema
5. erythema, edema and papules
6. vesicular eruption
7. strong reaction spreading beyond application site

Other Effects

- A. = slight glazed appearance
- B. = marked glazing
- C. = glazing with peeling and cracking
- D. = glazing with fissures
- E. = film of dried serous exudates
- F. = small petechial erosions and/or scabs
- G. = no other effects

The Subject Local Tolerability Assessment will be performed according to the Schedule of Visits and Assessments ([Section 1.3](#)).

At Day 1 only, local tolerability assessments should be recorded 10-15 minutes post-drug application for the Subject's '0-3' burning/stinging assessment.

The subject will assess burning/stinging (0-3 score), (For subjects <6 years of age, parents will complete.):

Grade	Sensation Following Drug Application
0 (none)	No sensation
1 (mild)	Slight warm, tingling sensation; not really bothersome
2 (moderate)	Definite warm, tingling sensation that is somewhat bothersome
3 (severe)	Hot, tingling/stinging sensation that has caused definite discomfort

This assessment will be administered by the study site at Day 1 and at every clinic visit.

- **Note: for subject burning stinging assessment at every clinic visit after Day 1, subjects will provide a recall assessment of burning/stinging experienced at most recent dosing.**

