^g At Day 1 only, local tolerability assessments should be recorded prior to study drug application for the investigator assessment of skin irritation (Berger and Bowman skin irritation score) and 10-15 minutes post-drug application for the Subject's '0-3' burning/stinging assessment. **Note for investigator tolerability assessments: reactions at the site of product application should be differentiated from the preexisting inflammation associated with the subject's atopic dermatitis. For subject tolerability assessments after Day 1, the subject will assess burning/stinging (0-3 score) 10-15 minutes post drug application based on recall of the last drug application.** For subjects <6 years of age, parents will complete.

^h Adolescents and adults (12 years and older) will complete the C-SSRS (12 years old of age and older). Adults will complete the PHQ-8. Adolescents (ages 12 to 17 years of age, inclusive) will complete the PHQ-A (PHQ-9 modified for Adolescents). Parents/caregivers will complete the parent report (CDI-2) for children 6-11 years of age, inclusive. Subjects will continue with the assessments specific to their age group at the time of consent/assent at Screening of the preceding study.

ⁱ The DLQI will be completed by subjects ≥17 years of age (based on age at start of preceding studies ARQ-151-311/312). The CDLQI will be completed for subjects ≥4 years of age and ≤16 years of age (based on age at start of preceding studies ARQ-151-311/312/315). The Infants' Dermatitis Quality of Life (IDQOL) will be completed by parents/caregivers for subjects <4 years (based on age at start of parent preceding studies ARQ-151-315). The Dermatitis Family Impact Questionnaire (DFI) will be completed by parents/caregivers for all subjects ≥ 2 years of age and ≤17 years of age. Subjects will continue with the assessments specific to their age group at the time of consent/assent at Screening of the preceding study. DFI is not to be conducted for subjects who were ≤17 years of age in the ARQ-151-311/312 studies and turned 18 years of age prior to enrollment into ARQ-151-313.

^j Photography will be performed using Canfield equipment on all subjects at all study sites. All efforts will be made to de-identify the subjects. Subjects who are unwilling to participate in the medical photography will be allowed to opt out of this procedure and documented on the informed consent. See Photography Manual for details.

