5.2 Baseline

There are two baseline definitions for the analyses:

- Primary baseline is defined as the last observation before or on the first dose of roflumilast cream 0.15% or 0.05% in ARQ-151 parent studies for subjects administered roflumilast previously and before or on the first dose of roflumilast cream 0.15% or 0.05% in this study* for subjects administered vehicle previously.
- OLE baseline is defined as the last observation before or on the first dose of roflumilast cream 0.15% or 0.05%* in this study.

If the last non-missing assessment was performed on the same date as the first dose of roflumilast cream* and time is not available, the assessment will be considered as baseline, except for adverse events (AEs) and medications starting on the first dose date which will be considered post-baseline. For subject local tolerability assessments, if the last non-missing assessment was performed on the same date as the first dose of roflumilast cream*, the assessment will be considered as baseline, regardless of the time of the assessment.

For the subjects administered vehicle in the parent study, the definition for Primary and OLE baselines are the same.

* Enrollment date (usually the Week 4 visit in the parent study) for enrolled subjects who discontinued early from this study before the first application of roflumilast cream 0.15% or 0.05%.

The following table ([Table 2](#)) described the baseline used in the analysis:

 Innovaderm Research	STATISTICAL ANALYSIS PLAN, Final Version 1.0
Protocol Number: ARQ-151-313	Sponsor: Arcutis Biotherapeutics, Inc.

Table 2 Summary of Primary/OLE Baseline in the Analyses

Analyses	Baseline*
Demographics and Baseline Characteristics	Primary baseline and OLE baseline, as applicable
Efficacy Analysis	Primary baseline and OLE baseline
Safety analysis for AEs and concomitant medications	OLE baseline
Safety analysis for clinical laboratory, vital signs, local tolerability assessments. PHQ-8, Modified PHQ-A, CDI-2, C-SSRS, and physical examination	Primary baseline

* Refer to Section 8 for more details.

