5.4 Windowing Conventions

The scheduled visit will be used to report measurements for summaries by visit regardless of whether this visit was performed within or outside of the analysis visit windows. Unscheduled visit, early termination (ET) visit, and/or retest measurements will only be used for the summaries by visit if a scheduled measurement is not available and the unscheduled/retest/ET measurement

 Innovaderm Research	STATISTICAL ANALYSIS PLAN, Final Version 1.0
Protocol Number: ARQ-151-313	Sponsor: Arcutis Biotherapeutics, Inc.

falls within the analysis visit windows described in [Table 3](#), [Table 4](#), [Table 5](#), and [Table 6](#). Scheduled, unscheduled, ET, and retest measurements will be listed.

If there is more than one assessment for a given analysis visit when a scheduled measurement is not available, the assessment closest to the target day will be considered. If two assessments are equidistant to the target day, the latest assessment will be used.

Table 3 OLE Analysis Visit Windows – vIGA-AD, EASI, BSA Affected by AD, DLQI, CDLQI, IDQOL, DFI, SCORAD, POEM, Vital Signs, Local Tolerability Assessments, PHQ-8, PHQ-A, CDI-2, and C-SSRS

Analysis Visit	Target Day	Window (Days)
OLE Week 4	29	15 to 57
OLE Week 12	85	58 to 127
OLE Week 24	169	128 to 211
OLE Week 36	253	212 to 309
OLE Week 52	365	≥ 310

Table 4 OLE Analysis Visit Windows – WI-NRS

Analysis Visit	Target Day	Window (Days)
OLE Week 1	8	5 to 11
OLE Week 2	15	12 to 18
OLE Week 3	22	19 to 25
OLE Week 4	29	26 to 32
OLE Week x	y	z1 to z2
OLE Week 52	365	≥ 362

where: x= 5 to 51; y= (x * 7) + 1; z1 = y – 3, and z2 = y + 3.

Table 5 OLE Analysis Visit Windows – Clinical Laboratory

Analysis Visit	Target Day	Window (Days)
OLE Week 24	169	15 to 267
OLE Week 52	365	≥ 268

 Innovaderm Research	STATISTICAL ANALYSIS PLAN, Final Version 1.0
Protocol Number: ARQ-151-313	Sponsor: Arcutis Biotherapeutics, Inc.

Table 6 OLE Analysis Visit Windows – Physical Examination

Analysis Visit	Target Day	Window (Days)
OLE Week 4	29	15 to 127
OLE Week 24	169	128 to 267
OLE Week 52	365	≥ 268

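### SAP 5.2 labels the subject's Day 1 burning/stinging score as baseline although it is taken 10-15 minutes after application, so vehicle roll-overs' reaction to their first roflumilast dose is reported as a pre-treatment value

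*SAP*

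**What the plan says.** Protocol 5.1.11 sets the timing. On Day 1, "local tolerability assessments should be recorded 10-15 minutes post-drug application for the Subject's '0-3' burning/stinging assessment". Footnote g to the schedule in SAP 3.3 repeats it: "10-15 minutes post-drug application for the Subject". The first open-label dose is given at that same visit. Protocol 4.7.3 has subjects apply the cream each evening "except on Day 1 when medication application will be done on site".

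SAP 5.2 has a general rule for same-day assessments: when no clock time is available, the assessment counts as baseline, "except for adverse events (AEs) and medications starting on the first dose date which will be considered post-baseline". A separate sentence then covers the subject's tolerability score. If it falls on the date of the first roflumilast dose, "the assessment will be considered as baseline, regardless of the time of the assessment".

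The same section says that Primary and OLE baseline are identical for subjects previously on vehicle. SAP Table 2 assigns Primary baseline to the local tolerability analyses. SAP 13.4 summarises the subject score by visit and treatment group, as category counts and descriptive statistics.

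**The concern.** A baseline value should describe the subject before exposure. This score is the subject's answer to how the cream felt a few minutes after it went on. For someone coming from vehicle, it is the only score collected directly after a first roflumilast application. Later clinic scores are recalled impressions of the most recent dose.

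Local tolerability is a listed safety endpoint (SAP 2). The protocol's background and rationale (2.1 and 2.4) cite burning and stinging as a drawback of the approved topical PDE-4 inhibitor and suggest that this cream may be better tolerated. If the first-dose reaction is classed as baseline, a reader of the by-visit table may take it for a complaint already present at entry. A statement confined to post-baseline visits would leave it out.

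**Working it through.** There is no sample-size, power or event figure to reproduce. The check is to follow one vehicle roll-over's Day 1 score through the rules.

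1. **Which study the score belongs to.** In the schedule of assessments (Protocol 1.3, SAP 3.3), the Day 1 local tolerability entry lacks the superscript s that marks values carried over from parent Week 4. It is a new measurement in this study.
2. **Study day.** SAP 5.3: Study Day = (assessment date − first-dose date) + 1. The score and the first open-label dose share a date, so Study Day = 0 + 1 = 1.
3. **Order within the day.** Application comes first and the score 10-15 minutes later (Protocol 5.1.11; SAP 3.3, footnote g). The order is known, so the general same-day rule for missing times is not needed.
4. **Classification in SAP 5.2.** The special sentence applies and overrides the known order. For a vehicle roll-over, Primary baseline is anchored to the first roflumilast dose in this study and equals OLE baseline. The Day 1 post-dose score is therefore the baseline.
5. **Against the protocol.** Protocol 4.3 and 5.1.1 define the safety baseline as the latest value recorded ahead of the first dose of active cream. A score taken after that dose cannot qualify. SAP 1 says departures from the protocol are described in SAP 3.6. The entries readable there concern tube weights, analyses by cohort and compliance on twice-weekly dosing; none covers this.
6. **Against the SAP's adverse event rule.** In SAP 5.2, adverse events starting on the first-dose date are post-baseline, and SAP 13.1 counts events starting after the Day 1 application as treatment-emergent. One stinging episode, if also recorded as an adverse event, would be treatment-emergent in one table and baseline in another.
7. **What is left as post-baseline.** The next scheduled clinic score is Week 4, target Day 29, which is 29 − 1 = 28 days after first exposure, and it is a recall score.
8. **Former-roflumilast subjects.** Their Primary baseline lies in the parent study, so their OLE Day 1 score is not that baseline. SAP 13.4 does not say under which visit it is shown. Whether their parent-study baseline score was also taken after application cannot be told from these documents.

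The investigator's irritation score is recorded before application on Day 1, so calling it baseline raises no such problem in vehicle roll-overs.

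**The case against.** The case for leaving the plan alone has real substance.

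- **No derived statistic is affected.** A reader might infer that the rule understates an on-treatment stinging rate. The documents do not support that: SAP 13.4 plans no change from baseline, shift table, worst post-baseline score or pooled on-treatment rate for this item. This stands, and it limits the point to classification and presentation.
- **The Day 1 score is not dropped by the visit windows.** SAP Table 3 covers "Local Tolerability Assessments, PHQ-8, PHQ-A, CDI-2, and C-SSRS" among other assessments, and its earliest window opens at Day 15. A reader might infer that a Day 1 score has nowhere to go. However, SAP 5.4 reports scheduled visits whether or not they fall inside a window; the windows place only unscheduled, early-termination and retest values. Scheduled measurements are also listed. This stands too. What remains is that the SAP names no Day 1 summary visit for the score.
- **The safety signal has another route.** Stinging recorded as an adverse event after the Day 1 application is treatment-emergent, and application-site events have their own table. That protects the primary safety endpoint, but it does not make the score a baseline value.
- **The columns already separate first exposure.** SAP 5 shows vehicle roll-overs apart from continuing roflumilast subjects. The remedy can use those columns; the wrong row category remains.
- **The table shells are in a separate document.** The row might be printed as Day 1 or carry a footnote. This cannot be checked, and the SAP's stated rule is baseline.

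**Conclusion.** The point holds as a classification error in SAP 5.2. For vehicle roll-overs, a reading taken after the first roflumilast application is defined as baseline, against the protocol's pre-dose definition and against the SAP's handling of same-day adverse events. SAP 5.2 gives no reason for the rule.

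Its size is modest. It concerns one item in the local tolerability summaries. It touches every vehicle roll-over with a Day 1 score, a number the documents do not give. No planned estimate or interval changes, and the primary safety endpoints are unaffected. The consequences are a post-dose value presented as pre-treatment, its absence from the post-baseline rows, and an unspecified place for former-roflumilast subjects' OLE Day 1 scores.

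The conclusion assumes that Day 1 scores are collected at the scheduled time and that the table shells follow SAP 5.2 as written.

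**What to change.** - In SAP 5.2, delete the sentence that makes the same-day subject tolerability score baseline whatever its time. State that the subject burning/stinging item has no pre-dose baseline.
- In SAP 13.4, report the scheduled Day 1 score as a post-dose visit, labelled for example *OLE Day 1, 10-15 min post-application*, for all roll-overs in the existing parent-treatment columns. This also settles where former-roflumilast subjects' scores appear.
- Keep the pre-application investigator score as baseline.

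The cost is a change of SAP wording and one relabelled row. No new data or assessments are needed. The downside for the sponsor is that the post-dose stinging results may look slightly less favourable.

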5.3 Study Day

Study Day will be calculated from the first dose of roflumilast cream 0.15% or 0.05%* in this study, and will be used to show start/end day of assessments or events.

Study Day = (Date of assessment/event – Date of first dose of roflumilast cream in this study) + 1
if date of assessment/event is on or after the date of first dose of roflumilast cream in this study;
= (Date of assessment/event – Date of first dose of roflumilast cream in this study) if date of assessment/event is before the date of first dose of study roflumilast cream in this study.

* Enrollment date (usually the Week 4 visit in the parent study) for enrolled subjects who discontinued early from this study before the first application of roflumilast cream 0.15% or 0.05%.

In the situation where the assessment/event date is partially or completely missing, Study Day will be missing.

5.4 Windowing Conventions

The scheduled visit will be used to report measurements for summaries by visit regardless of whether this visit was performed within or outside of the analysis visit windows. Unscheduled visit, early termination (ET) visit, and/or retest measurements will only be used for the summaries by visit if a scheduled measurement is not available and the unscheduled/retest/ET measurement

 Innovaderm Research	STATISTICAL ANALYSIS PLAN, Final Version 1.0
Protocol Number: ARQ-151-313	Sponsor: Arcutis Biotherapeutics, Inc.

falls within the analysis visit windows described in [Table 3](#), [Table 4](#), [Table 5](#), and [Table 6](#). Scheduled, unscheduled, ET, and retest measurements will be listed.

If there is more than one assessment for a given analysis visit when a scheduled measurement is not available, the assessment closest to the target day will be considered. If two assessments are equidistant to the target day, the latest assessment will be used.

Table 3 OLE Analysis Visit Windows – vIGA-AD, EASI, BSA Affected by AD, DLQI, CDLQI, IDQOL, DFI, SCORAD, POEM, Vital Signs, Local Tolerability Assessments, PHQ-8, PHQ-A, CDI-2, and C-SSRS

Analysis Visit	Target Day	Window (Days)
OLE Week 4	29	15 to 57
OLE Week 12	85	58 to 127
OLE Week 24	169	128 to 211
OLE Week 36	253	212 to 309
OLE Week 52	365	≥ 310

Table 4 OLE Analysis Visit Windows – WI-NRS

Analysis Visit	Target Day	Window (Days)
OLE Week 1	8	5 to 11
OLE Week 2	15	12 to 18
OLE Week 3	22	19 to 25
OLE Week 4	29	26 to 32
OLE Week x	y	z1 to z2
OLE Week 52	365	≥ 362

where: x= 5 to 51; y= (x * 7) + 1; z1 = y – 3, and z2 = y + 3.

Table 5 OLE Analysis Visit Windows – Clinical Laboratory

Analysis Visit	Target Day	Window (Days)
OLE Week 24	169	15 to 267
OLE Week 52	365	≥ 268

 Innovaderm Research	STATISTICAL ANALYSIS PLAN, Final Version 1.0
Protocol Number: ARQ-151-313	Sponsor: Arcutis Biotherapeutics, Inc.

Table 6 OLE Analysis Visit Windows – Physical Examination

Analysis Visit	Target Day	Window (Days)
OLE Week 4	29	15 to 127
OLE Week 24	169	128 to 267
OLE Week 52	365	≥ 268

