5.6. Unscheduled Visit

Beginning at the Week 4 visit, any subject who achieves vIGA-AD of ‘0-clear’ as confirmed by the Investigator at a scheduled or unscheduled clinic visit, will switch to twice weekly (BIW) maintenance treatment. For maintenance therapy, study medication will be applied on two nonconsecutive days per week (e.g. Monday and Thursday) to areas commonly and/or most recently affected by AD, and any areas where AD is developing. Subjects receiving maintenance treatment who experience AD worsening (signs and symptoms) for 1 week despite dosing twice weekly will phone the clinical study site, resume daily dosing, and complete the subject diary accordingly. The phone call (but not a clinic visit) is required to resume daily dosing.

Unscheduled visits may be necessary to repeat testing following abnormal laboratory results, for follow-up of AEs, or for any other reason, as warranted in the judgement of the Investigator.

The following information will be collected for all subjects:

- Concomitant medications/procedures
- AEs

The following information also will be collected:

- vIGA-AD and EASI
- BSA affected with AD
- Local tolerability assessment (by Investigator)

However, if an unscheduled visit is required for reasons other than safety (e.g. procedures such as labs or images that were either missed at the regular subject visit or need to be repeated), the vIGA-AD and EASI, BSA affected with AD, and Local Tolerability assessment (by Investigator) are not required.

The rules for how to tally vIGA-AD, BSA or other proportions of categorical responses will be described in the Statistical Analysis Plan.

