5.9. Treatment Stopping Rules

If a subject has non-cutaneous adverse events of concern, clinically significant laboratory values or any condition that the investigator determines could possibly be related to the study drug, the Investigator should immediately contact the Medical Monitor to discuss if the subject should be discontinued from treatment with investigational product.

Treatment for any individual subject will be discontinued if the subject experiences:

- A serious adverse event (SAE) or a clinically significant non-serious AE which in the opinion of the Principal Investigator or Medical Monitor warrants discontinuation from the study for that subject's well-being.
- A severe (Grade 3) laboratory abnormality (confirmed by repeat sample and considered related to study drug [\[Appendix 12\]](#)).

A subject with a PHQ-8 or modified PHQ-A score ≥ 15 should receive immediate referral to a mental health professional, and Investigators in consultation with the mental health professional should consider interruption or discontinuation of the study drug.

A subject with a CDI-2 raw total score of ≥ 32 should be referred to a mental health professional, and Investigators in consultation with the mental health professional should consider interruption or discontinuation of the study drug.

A subject 2 to 5 years of age that is exhibiting behavioral changes that may signal psychological or emotional distress should be evaluated immediately by the investigator to determine if referral to a qualified mental health care provider is necessary, and consideration should be given to discontinuing study drug.

A subject that is experiencing suicidal ideation and behavior should be referred immediately to a qualified mental health care provider and consideration given to discontinuation from study drug.

As noted above, study treatment must be discontinued immediately in the event of a female subject's pregnancy.

Treatment should be interrupted:

- If a subject develops an application site reaction with the clinical appearance of an 'irritation reaction', and with a severity of a Dermal Response Score of 5 (erythema, edema and papules) or greater on the scale of Berger and Bowman, treatment should be interrupted for up to one week and may then be resumed if the reaction has, in the opinion of the Investigator, adequately resolved.

Treatment should be discontinued:

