6.9. Clinical Laboratory Results and Vital Signs

All clinical laboratory results (subjects ≥ 12 years old) and vital signs measurements will be summarized descriptively by parameter, visit, and treatment group along with time point of collection.

A shift from baseline table describing out-of-normal range shifts will be provided for clinical laboratory results.

A shift from baseline table will identify subjects who gain or lose $>5\%$ body weight over the course of the study.

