5.8 Handling of Retests, Unscheduled Visits, and Early Termination Data

Retests measurements, unscheduled measurements, and ET visit assessments will be included in analysis and be summarized via analysis visit windowing according to the windowing conventions in section 5.4.

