13.3 Vital Signs

For each vital sign (systolic blood pressure, diastolic blood pressure, heart rate, body temperature, weight, and height for subjects <18 years), observed values, changes from primary baseline and percent changes from primary baseline will be summarized descriptively by visit and treatment group as defined in Section 5.

The number and percentage of subjects with a gain or lose $>5\%$ in body weight from primary baseline to each OLE post-baseline visit will be summarized by visit and treatment group as defined in Section 5. A similar summary further broken down by age group (refer to Section 6.6) will also be provided.

For adults (≥ 18 years), the BMI observed values will be summarized using descriptive statistics by treatment group as defined in Section 5. For children (2 to 11 years) and adolescents (12 to 17 years), the BMI percentile rather than BMI observed value will be summarized using descriptive statistics by treatment group as defined in Section 5.

A listing of all vital sign assessments, including weight and BMI, will be provided.

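### The by-visit tolerability table drops an unscheduled or ET dermal-response score whenever the scheduled score for that window exists, and no planned table counts subjects who ever scored 5 or more; separately, the whole-study count of >5% weight change has become a per-visit count

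*SAP*

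**What the plan says.** **Which score enters the table.** SAP 5.4 gives the scheduled visit priority: "The scheduled visit will be used to report measurements for summaries by visit regardless of whether this visit was performed within or outside" the analysis windows. Unscheduled, ET and retest "measurements will only be used for the summaries by visit if a scheduled measurement is not available" and they lie inside a window. If several compete, the one nearest the target day is taken, and on a tie the latest. SAP 5.8 opens no other route: these data are to "be included in analysis and be summarized via analysis visit windowing according to the windowing conventions in section 5.4". SAP 5.4 also provides that "Scheduled, unscheduled, ET, and retest measurements will be listed".

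**What is tabulated.** SAP 13.4 summarises dermal response (0 to 7) by visit and treatment group, as categories and as a continuous score. It plans no maximum and no any-time count.

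**Where between-visit scores come from.** Protocol 5.6 includes "Local tolerability assessment (by Investigator") among the items collected at unscheduled visits, and waives it when the visit is for reasons other than safety. It leaves the rules for tallying categorical responses to the SAP. Protocol 5.5 gives an ET visit the Week 52 procedures, which include local tolerability. Under Protocol 5.9, for an irritation reaction with a dermal response of 5 or more, "treatment should be interrupted for up to one week and may then be resumed if the reaction has" resolved adequately in the investigator's opinion.

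**Weight.** Protocol 6.9 plans a shift table identifying subjects who gain or lose more than 5% of "body weight over the course of the study". SAP 13.3 instead counts subjects with a change of more than 5% in "body weight from primary baseline to each OLE post-baseline visit will be summarized by visit" and treatment group.

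**The concern.** An unscheduled safety visit takes place because something has happened. For dermal response, the rule lets a routine score from another day, often weeks later, stand in for the score taken during the reaction. Interruption lasts up to a week, while clinic visits are 4 to 16 weeks apart, so a reaction can reach the protocol's own threshold and resolve before the next scheduled score.

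Long-term safety is the primary objective and local tolerability is a named safety endpoint in SAP Section 2. Yet the report would contain no rate, with a denominator, of subjects who ever scored 5 or more.

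The weight point is similar in kind. Protocol 2.3.2 names weight loss among the most common adverse events of oral roflumilast. Per-visit counts do not say how many subjects were ever affected.

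**Working it through.** **1. The plan's own windows.** SAP Table 3 target days are 29, 85, 169, 253 and 365. Taking Day 1 as the start, the midpoints are:
- (1+29)/2 = 15
- (29+85)/2 = 57
- (85+169)/2 = 127
- (169+253)/2 = 211
- (253+365)/2 = 309

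These reproduce the tabulated bounds (15-57, 58-127, 128-211, 212-309, 310 and later). The lower bound of 15 leaves Days 2-14, 13 days, in no window.

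**2. Which between-visit days can supply a score.** With visits on their target days, Cohort-Week 52 has 364 days (Days 2-365) less 5 visit days = 359 between-visit days. Cohort-Week 24 has 168 - 3 = 165.
- All scheduled scores present: 0 of 359 and 0 of 165 days are eligible.
- Scheduled score missing with probability m at each visit (assumed): the eligible share is m × (359-13)/359 or m × (165-13)/165.

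| Assumed m | Cohort-Week 52 | Cohort-Week 24 |
|---|---|---|
| 5% | 4.8% | 4.6% |
| 10% | 9.6% | 9.2% |
| 20% | 19.3% | 18.4% |

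An ET score is not safe either. A subject seen at Week 4 on Day 29 who leaves on Day 50 has an ET score in the 15-57 window, where the scheduled score already exists, so the ET score is not used.

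**3. How often a scheduled visit would catch the reaction anyway.** Neither document gives a reaction duration. Assume uniform onset and L days of visibility; the chance that the visit ending a gap falls inside the reaction is L divided by the gap.

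| Interval | Gap (days) | L = 7 | L = 14 |
|---|---|---|---|
| Weeks 0-4 | 28 | 25% | 50% |
| Weeks 4-12 | 56 | 12.5% | 25% |
| Weeks 12-24 | 84 | 8.3% | 16.7% |
| Weeks 24-36 | 84 | 8.3% | 16.7% |
| Weeks 36-52 | 112 | 6.3% | 12.5% |

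Over 52 weeks, five visits give 5×7/364 = 9.6% for 7 days and 5×14/364 = 19.2% for 14 days. For Cohort-Week 24 the figures are 3×7/168 = 12.5% and 3×14/168 = 25%.

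The remainder is not the share lost through SAP 5.4. A reaction that prompts no unscheduled or ET visit has no score to lose. The recoverable share is the remainder multiplied by the proportion that prompt such a visit, and the documents do not give that proportion.

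**4. Weight.** If n₁ to n₅ subjects exceed 5% at the five visits, the number ever exceeding it lies anywhere between the largest nᵢ and the sum of the nᵢ (capped at the number of subjects). The per-visit table cannot fix it within that range. SAP Section 1 says that changes from the protocol are described in Section 3.6, whose entries concern tube-weight categories, analysis by cohort and compliance criteria. Weight change is not among them.

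**The case against.** The strongest defence is that the harm is captured elsewhere. AEs and SAEs are the primary endpoints, the AE definition in Protocol 5.7.1 is broad, and SAP 13.1 tabulates application-site TEAEs and TEAEs leading to treatment discontinuation regardless of visit windows, with exposure-adjusted rates. Every unscheduled score is listed. The by-visit format is also what Protocol 6.8 specifies, so SAP 13.4 departs from nothing.

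This stands in part. The reaction is likely to be visible somewhere, and the tolerability table follows the protocol. But neither document says that a dermal response of 5 or more must be recorded as an AE. AE severity is graded on CTCAE, not the dermal scale, and no table is planned for TEAEs leading to interruption. A listing gives no rate.

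Four stronger readings are tempting, and the documents do not support them.
- **That between-visit reactions never reach the table.** This is strictly true only of unscheduled or ET scores on Days 2-14. From Day 15 such a score can enter when the scheduled one is missing, and a reaction still present at a scheduled visit is scored there.
- **That stopping treatment in the first two weeks leaves no post-baseline score.** Protocol 4.7.5 and 4.7.6 separate stopping treatment from leaving the study. A subject who stays still contributes a Week 4 score; the gap arises on leaving.
- **That 88-94% of reactions are lost.** That range is the complement of 12.5% to 6.3%. It rests on an assumed 7-day duration, leaves out Weeks 0-4 (where 75% would be missed), and includes reactions that were never scored.
- **That the rule hides harm in every safety domain.** Protocol 5.6 gives repeat testing after an abnormal laboratory result as a reason for an unscheduled visit; there, preferring the scheduled value often keeps the abnormal result. Its list of items for unscheduled visits includes neither weight nor burning/stinging, so little unscheduled data exist in those domains to be displaced.

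On weight, a reader could take a set of per-visit counts as covering the course of the study. Step 4 shows that it does not identify who was ever affected.

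**Conclusion.** The point holds for investigator dermal response. An unscheduled or ET score is left out unless the scheduled score for its window is missing and the assessment is on or after Day 15. A score that triggered interruption can thus be replaced by a scheduled one and survive only in a listing. This follows from SAP 5.4, 5.8 and 13.4 without any assumption.

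The size is less certain. Under the 7-day, uniform-onset assumption, scheduled visits alone would coincide with roughly one reaction in ten over 52 weeks. How much an any-time summary would recover depends on an unscheduled-visit frequency that is not stated.

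The weight point is separate and is a mismatch between the documents: the SAP narrows a protocol commitment without declaring it. Both deserve correction. Neither affects a hypothesis test, since SAP 5.7 plans none.

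**What to change.** - **SAP 13.4:** keep the by-visit table. Add a worst post-baseline dermal-response summary from all scheduled, unscheduled and ET assessments after the first OLE dose, without window restriction. Include the number and percentage of subjects with a score of 5 or more at any time.
- **SAP 13.3:** keep the per-visit counts. Add the number and percentage of subjects with a weight gain above 5%, and with a loss above 5%, at any OLE post-baseline assessment. Show gain and loss separately and by the age groups already used there, because growth will produce gains in children. If the whole-study count is deliberately dropped, record that in SAP 3.6.
- **Optional:** rows for maximum burning/stinging and worst laboratory shift. SAP 5.2 treats a burning/stinging score on the first-dose date as baseline whatever its time, so any maximum should say how that score is handled.

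The data are already collected. The cost is SAP wording, a few extra rows and somewhat less favourable reported rates.
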